3.6 DATA ANALYSIS

All analyses will be conducted separately within each database.

3.6.1 Main analyses

Analyses in this protocol are inherently descriptive in nature. The analyses described below will initially be conducted for the base cohort (Jan 2009- June 2012 data). Analyses will be updated at 6-month intervals as more data become available for the existing cohort(s) and new users are identified within the additional time period (July 2012- Dec 2015 data). As new data become available, we will characterize the patients newly initiated on treatment during that time period separately, in order to enable characterization of the shift in patient characteristics and use over time. In addition, short and long-term outcomes for the already existing cohorts (i.e., patients identified in previous time periods) will be updated with the newly available information in terms of switches, discontinuations, adherence and persistence.

A 12-month time window of no treatment is used to define a “new” treatment episode (i.e., incident user). Patients who re-initiate treatment after a treatment gap of \geq 12 months will re-enter the cohort as former users.

Primary outcomes:

Treatment initiation over time:

The yearly anticoagulation initiation rate will be estimated as the proportion of patients who initiated treatment among the source cohort of patients with non-valvular atrial fibrillation who met the study inclusion criteria and were not already on treatment. To identify the

source cohort of treatment candidates in a given calendar time window (i.e., the denominator for the rate), all patients with at least one day eligibility will be identified. A random date within the first eligibility period (if more than one) within the calendar time window will be selected and set as the index date. The cohort inclusion and exclusion criteria will be evaluated using this index date. Patients who were dispensed an anticoagulant before the assigned index date (prevalent users) will be removed from the denominator, unless they are identified as new initiators (i.e., included in the numerator) for that particular time period.

Characteristics of anticoagulant users:

The analyses will describe the proportion of patients treated with various oral anticoagulants, as well as the characteristics of these patients. For the NOACs, the starting dose will also be considered. Analyses will be conducted

as well for the combined cohort of incident and former users. Characteristics for the combined cohort will be presented in the core set of tables;

—
—
—

Data prior to the launch of dabigatran in October 2010 will be used to characterize warfarin patients before the NOACs became available, and to evaluate the potential shift in patient characteristics over time. A comparison of patient characteristics across treatment groups will only be conducted within a common time window.

Secondary outcomes:

Utilization measures: Non-persistence

To ensure a valid comparison of utilization measures ([Table 3](#)), patients exposed to the various NOACs will be matched to warfarin on an exposure propensity score (PS) in a 1:1 fixed ratio using a nearest neighbor technique and a caliper of 0.05. In addition, the patients

will be matched within calendar quarters (3 month periods).

Briefly, all covariates listed in [REDACTED] will be included in a logistic regression propensity score (PS) model without further variable selection. In addition to demographic information, variables included in the PS were identified based on the a-priori expectation that they might be both associated with choice of anticoagulant and risk factors for study outcomes so that they represent likely confounding variables in a comparative safety and effectiveness analysis. The underlying assumption is that these variables capture the most important predictors of treatment persistence.

Balance of baseline characteristics in the matched cohorts will be evaluated. The utilization measures included in [Table 3](#) will be described for the PS-matched cohort. To properly account for differential follow-up, survival type analyses (i.e., Kaplan-Meier) will be used to describe time from treatment initiation to non-persistence (discontinuation or switch).

Number of patients at risk for this treatment outcome will be provided at 3-month intervals.

The various analyses are summarized below:

Analysis	Population	Outcome measure	Outcome type
Treatment initiation over time	Source population	Yearly initiation rate	Primary
Characteristics of anticoagulant users	Treatment cohort - Unmatched - Matched	Baseline characteristics	Primary
Utilization measures	Matched treatment cohort	- Treatment non-persistence (KM)	Secondary

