3.2 STUDY POPULATION

From the UnitedHealth Research Database and MarketScan source data, we will identify patients with a recorded diagnosis of non-valvular atrial fibrillation at risk for stroke who initiated anticoagulant medications between January 2009 and June 2012. Additional increments of data will be added as they become available (in 6 month intervals). Data from the time period before dabigatran was launched will be used to describe the characteristics of warfarin patients before the availability of NOAC, and to evaluate a potential shift in characteristics of warfarin patient over time as NOAC enter the market.

Inclusion criteria²:

- Any person within the source data who had a diagnosis of atrial fibrillation recorded (ICD-9 Dx code of 427.31, atrial fibrillation) and received a dispensing of an anticoagulant medication (warfarin and dabigatran for the initial analysis; with others to be added as they become available for stroke prevention in later time intervals) in the timeframe of the study.
- The first dispensing is preceded by at least 12 months continuous enrollment in the study database, defined as <32 days enrollment gap using enrollment and disenrollment dates. The study will thus focus on 'new initiators' defined operationally as no dispensing of any anticoagulant in the prior 12 months. Note that new initiators will turn into prevalent users over time.
- Patients' follow-up will end when there is a treatment gap of ≥ 30 days. If the same patient re-initiates treatment later on – after a treatment gap of ≥ 12 months –, (s)he may re-enter the cohort at that time (an indicator variable will be created to identify such patients, known as former users).
- 18 years or older at the time of treatment initiation
- CHA₂DS₂-VASc score³ ≥ 1

Exclusion criteria:

- patients with less than 12 months continuous enrollment in the study database without anticoagulant use before the first dispensing of anticoagulant medication.
- Patients with missing or ambiguous age or sex information.
- Patients with documented evidence of valvular disease defined as at least 1 inpatient or outpatient ICD-9 Dx code of [R11-4334]
 - 394.x (diseases of mitral valve)
 - 395.x (diseases of aortic valve)
 - 396.x (diseases of mitral and aortic valve)
 - 397.x (diseases of other endocardial structures)
 - 398.9x (other and unspecified rheumatic heart diseases)
 - V42.2 (heart valve replaced by transplant)

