3.4 OUTCOMES

Patterns of anticoagulant medication use will be identified on the basis of a pharmacy dispensing. Pharmacy dispensing is considered the most accurate utilization measure short of electronic pillcounting caps. [\[R13-0543\]](#)

The primary outcomes considered include the proportion of patients dispensed specific anticoagulants and anticoagulant doses (for NOAC), as well as a description of the characteristics of these patients.

In addition, a variety of measures will be derived from features of the dispensing data, including: number of dispensings, characteristics of dispensings (dose, and days supplied), along with persistence measures (e.g., proportion with a single dispensing, proportion remaining on therapy over time, time until treatment switch or discontinuation). [\[R13-0542; R12-3689; P06-11504\]](#)
Treatment persistence over time constitutes the secondary outcome,

Table 3

[figure not shown]
Definition of utilization measures

Measure	Definition
Days supplied*	Number of days supplied by a dispensing
Dose**	Presumed dose based on # tablets, mg per tablet, and number of days
One dispensing only	Number (and fraction) of first anticoagulant recipients with no second dispensing
Persistence	Fraction of anticoagulant users with continued dispensings. Patients will be classified as persistent if they possess medication at the specified time point. Grace period of 14 days will be allowed to obtain an additional refill.
Anticoagulant switch	Dispensing of another anticoagulant within <30 days of the end of days supplied of the previous medication
Anticoagulant discontinuation	Treatment gap of ≥ 30 days (i.e., no dispensing of anticoagulant medication within 30 days of the end of days supplied)

*: Days supply likely reflects use patterns in a commercial insurer such as United Health or MarketScan.

**: Estimation of dose will be challenging during the dose titration period for warfarin. We explore warfarin dose over time and assess the feasibility of estimating average dose, seeking to identify maintenance dose (i.e., dose needed for consistent therapeutic INR).

***:

Notes:

Incident user: Patient with no dispensing of an oral anticoagulant in the prior 12 months

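### The denominator rule for the yearly initiation proportion states no look-back and keeps earlier users only if they are counted as initiators; a 12-month look-back is the likelier intent and would leave a small remainder

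*Combined protocol and SAP*

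**What the plan says.** Section 3.6.1 defines the yearly initiation rate as the proportion starting an anticoagulant among patients with non-valvular atrial fibrillation "who met the study inclusion criteria and were not already on treatment". Each candidate gets a random index date in the calendar window. "The cohort inclusion and exclusion criteria will be evaluated using this index date". Patients are then handled as follows: those "dispensed an anticoagulant before the assigned index date (prevalent users) will be removed from the denominator, unless they are identified as new initiators", meaning that they are in the numerator for that period.

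Four other places bear on the rule.

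- Section 3.2 defines a new initiator by the absence of any anticoagulant dispensing in the prior 12 months. The notes to Table 3 in Section 3.4 agree: "Incident user: Patient with no dispensing of an oral anticoagulant in the prior 12 months".
- Patients who restart after a gap of at least 12 "months will re-enter the cohort as former users" (Section 3.6.1; Section 3.2 is similar).
- Appendix 1 presents the core tables, including Core Table 1 on initiation over time, for incident and former users combined unless their characteristics differ meaningfully.
- The synopsis excludes patients with prior use of any oral anticoagulant and sets no time limit.

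**The concern.** A former user who has been off treatment for 12 months or more is not on treatment, and on restarting meets the new-initiator definition. Such a patient is a treatment candidate and belongs in the denominator whether or not treatment restarts. Under the removal sentence as worded, the earlier dispensing takes the patient out, and only a restart brings the patient back. Membership of the denominator then depends on the outcome. Among these former users the initiation proportion would be 100% whatever the true restart rate.

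The measure is a primary outcome and is repeated with updated data in each six-monthly report (Section 8). Two programmers could also build different denominators from the same paragraph, and the validation described in Section 6 cannot settle a rule that the protocol leaves open.

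**Working it through.** **Plan's own figures.** The documents give no expected initiation proportion, denominator or former-user share, so there is no figure to reproduce for this measure. Table 1 in Section 3.2.1 supplies a yardstick. Its formula √(p(1−p)/n) at p = 10% gives √(0.1×0.9/10,000) = 0.3 points, and 0.1 points at n = 100,000, as printed.

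**Is a look-back implied?**

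- The removal sentence glosses the removed patients as prevalent users.
- The Table 3 notes define a potential prevalent user as someone with under 12 months' enrolment before the first observed dispensing. The reason given is that such a patient could have been treated in the prior 12 months. This implies that a prevalent user is someone treated in those 12 months.
- Section 3.2 is looser: "Note that new initiators will turn into prevalent users over time". It gives no end point.

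Twelve months is therefore the likelier intent, but the rule does not say so.

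**Literal rule (all inputs assumed).** Let f be the former-user share of eligible patients and r the initiation proportion, equal in former users and others.

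Reported = r / [(1−f) + f·r]

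With 10,000 eligible patients, f = 5% and r = 10%, 1,000 initiate. Of the 500 former users, 450 do not restart and are removed. The report shows 1,000/9,550 = 10.5% in place of 10.0%.

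| f | r = 5% | r = 10% | r = 20% |
|---|---|---|---|
| 2% | 5.1% | 10.2% | 20.3% |
| 5% | 5.2% | 10.5% | 20.8% |
| 10% | 5.5% | 11.0% | 21.7% |
| 20% | 6.2% | 12.2% | 23.8% |

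The 10% and 20% shares are upper illustrations, since Section 4 puts average patient history at about 2 years.

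If former users restart at a different proportion q, with f = 5% and 10% initiation in the others:

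- q = 5%: true (0.95×0.10 + 0.05×0.05) = 9.75%; reported 0.0975/0.9525 = 10.24%.
- q = 20%: true (0.95×0.10 + 0.05×0.20) = 10.5%; reported 0.105/0.96 = 10.94%.

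**With a 12-month look-back.** A patient who reaches 12 drug-free months inside the window, but after the random date, has a dispensing in the 12 months before that date. The patient is removed unless a restart follows. Let g be the share reaching 12 drug-free months in the window, half of them after their random date.

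Reported = r / [1 − 0.5·g·(1−r)]

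At r = 10%, g = 1%, 2% or 5% gives 0.10/0.9955 = 10.05%, 0.10/0.991 = 10.1% or 0.10/0.9775 = 10.2%.

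**Net direction.** Section 3.6.1 does not settle whether initiators must also meet the other criteria on the random date. Suppose they must, and keep the literal removal rule with f = 5% and 10% restarting. Let a share i of the other patients be newly diagnosed in the window and initiate at 20%, and let the rest initiate at 10%. With uniform dates, half of the newly diagnosed fail on their random date and leave both numerator and denominator.

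- True = 0.95[0.2i + 0.1(1−i)] + 0.005
- Reported = {0.95[0.1(1−i) + 0.1i] + 0.005} / {0.95[(1−i) + 0.5i] + 0.005}

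| i | True | Reported | Difference (points) |
|---|---|---|---|
| 10% | 10.95% | 11.02% | +0.07 |
| 20% | 11.90% | 11.63% | −0.27 |
| 30% | 12.85% | 12.31% | −0.54 |

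The net error can have either sign.

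**The case against.** The strongest reply is that the 12-month window runs through the whole protocol, and that the literal reading isolates one sentence from its definitions. The Table 3 notes support this, and the criteria are to be applied at the index date. With that look-back the remainder is 0.05 to 0.2 points in the illustrations. That is below the 0.3-point standard error at n = 10,000, although the largest value exceeds the 0.1 points at n = 100,000. The analyses are descriptive, and no test depends on the rate. The exemption also has a proper use: it keeps patients who first initiate before their random date. Figure 2 is not available in the text reviewed, and other parts of Section 3.6.1 have gaps.

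Most of this stands, and it reduces the size of the point. It does not remove it. The paragraph holding the removal rule appears complete and states no look-back, and under either reading some earlier users are kept only if they restart.

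One could also argue from the synopsis that former users are outside the population, so that the fault lies in counting them in the numerator. Sections 3.2 and 3.6.1 expressly let them re-enter, so the documents conflict here and neither side can simply be assumed.

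**Conclusion.** The rule should be corrected. As worded, it selects part of the denominator of a primary outcome on the outcome itself. A 12-month look-back is probably intended, and it would reduce the problem to patients who reach 12 drug-free months after their random date. On assumed inputs, a true 10.0% then reads 10.05% to 10.2%. Under the literal rule it reads 10.2% to 12.2% for former-user shares of 2% to 20%. None of these sizes can be derived from the documents.

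A reader might infer that the reported rate is too high overall. The documents do not support that. The upward direction holds for this component only, and the net check gave +0.1 to −0.5 points under one unsettled reading of eligibility.

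A reader might also infer that the calendar trend is distorted. The number of observable former users could change as data accumulate, but no counts are given, so this remains a possibility only.

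**What to change.** 1. Limit the prevalent-user removal to dispensings in the 12 months before the index date, matching the new-initiator definition.
2. Treat former users the same way in numerator and denominator. Either keep every otherwise eligible former user who reaches 12 drug-free months in the window, whether or not treatment restarts and even where step 1 would remove the patient, or drop former users from both. In the 5% example both options restore 10.0%: 1,000/10,000 or 950/9,500. They agree there because former users were assumed to restart at the common 10%. If they restart at 5%, the first option gives 9.75% and the second 10.0%, so the choice defines what is being estimated and should be stated.
3. Keep the exemption for patients without earlier use who initiate in the window before their random date. Apply the same other eligibility criteria to initiators and non-initiators. The exception is the part of the first inclusion criterion in Section 3.2 that requires the patient to have met the diagnosis criterion "and received a dispensing of an anticoagulant medication", which non-initiators cannot satisfy.
4. Align the synopsis exclusion on prior use with the choice made in step 2.

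The random index date need not be replaced. The cost is rewording one paragraph and the matching synopsis line, and reprogramming Core Table 1 from enrolment, diagnosis and dispensing dates already held. The reported proportion may be slightly lower.

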PROTOCOL CHANGES

Informed by the first two analyses (Interim Report 1 and 2), the analyses were streamlined to remove redundant information and focus on the main outcomes of interest. The specific changes are documented in the table below.

Date	Versi on	Type of Change	Comments
31 July 2014	V 2.0	Addition of MarketScan data throughout the document	Added to increase the population size (Synopsis, Study design, Data Sources 3.1)
31 July 2014	V 2.0	Treatment gap to define end of follow-up changed from 6 months to 30 days	Many patients will be censored for administrative reasons before they reach a 6-month treatment gap, reducing the opportunity to observe between-treatment differences. Treatment discontinuation will therefore be evaluated using a 30 day treatment gap instead in the main analysis,
31 July 2014	V 2.0	Prevalence of use was changed to treatment initiation rates	Change implemented to streamline the analyses and focus on the main outcomes of interest (Main analyses 3.6.1)
31 July 2014	V 2.0		
31 July 2014	V 2.0	Persistence over time is considered a secondary outcome	Informed by the first analyses, persistence over time is considered of high importance to describe anticoagulant utilization (Outcomes 3.4 and Main analyses 3.6.1)
31 July 2014	V 2.0	12-month covariate	The covariate assessment period was changed from 6 months to one year for

		assessment period	consistency with the comparative safety protocol (Covariates 3.5)
31 July 2014	V 2.0	Utilization measures are examined in a propensity-matched cohort	To ensure a valid comparison of utilization measures, these measures are examined in a propensity-score matched cohort, rather than in the overall study population (Main analyses 3.6.1)
31 July 2014	V 2.0		
31 July 2014	V 2.0		

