3.2.1 Study size

This study will be estimating anticoagulant utilization parameters within a sampled population. The precision of these estimates will depend on the numbers of patients on which the estimate is made, and features of the estimate itself. The number of patients receiving anticoagulant medication and meeting study selection criteria is unknown at this stage. However, we assume that between 10,000 and 15,000 patients per year will meet selection criteria as having used warfarin or a newer anticoagulant so that by the end of the study (data from 2009-2015), there will be a total of at least 100,000 patients in each data source. (source: These are projections based on preliminary counts in the available UnitedHealth data)

The precision of proportion estimates (e.g. prevalence) is a function of the proportion and the number of patients contributing to the proportion (precision = standard error = $\sqrt{p(1-p)/n}$). As indicated in the table below, across a range of estimates provided, the precision for a prevalence estimate of 10% or 20% is less than 5% even for sample sizes that will likely be present in subgroups described in this study.

Table 1 Precision of estimates for proportion measures

Numerator	Denominator	Prevalence	95% CI	Precision (s.e.)
10	100	10%	4.9%-17.6%	3.0%
100	1,000	10%	8.2%-12.0%	0.9%
1,000	10,000	10%	9.4%-10.6%	0.3%
10,000	100,000	10%	9.8%-10.2%	0.1%
20	100	20%	12.7%-29.2%	4.0%
200	1,000	20%	17.6%-22.6%	1.3%
2,000	10,000	20%	19.2%-20.8%	0.4%
20,000	100,000	20%	19.8%-20.2%	0.1%

For continuous measures such as medication possession ratio ((MPR), see [Table 3](#)), the precision depends on the number of subjects on whom the estimate is made and the variability of the measures (precision = standard error = $\sqrt{\text{standard deviation}^2/n}$). As indicated in the table, the precision for a continuous measure is 5% or less even for measures that apply to strata that represent subgroups to be defined in this study.

Table 2

Precision of estimates for continuous measures

Sample Size	Mean	SD	Precision (s.e.)
100	1	0.5	5.0%
1,000	1	0.5	1.6%
10,000	1	0.5	0.5%
100,000	1	0.5	0.2%

By the end of the study, with a projected 100,000 patients meeting selection criteria, the various adherence measures will be estimated with a precision of 1% or less, except within fairly small strata.

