8. STUDY MILESTONES AND RESPONSIBILITIES

Date	Phase 3		Data Source	
	Milestone	Month	United	MarketScan
			Claims and lab data are released every 6 months in Jan and Jul (6-month lag time)	Claims data are released quarterly in Mar, Jun, Sept, and Dec (9-month lag time) Lab data are released yearly in Dec (12-month lag time)
Year 1				
Jun, 2012	Contract	0		
Jul, 2012	Draft Protocol	1		
Mar, 2013	Protocol finalization	9		
Year 2				
Jun, 2013	Draft Interim Report*	12	Jun, 2012	
Aug, 2013	Interim Report	14	Jun, 2012	
Dec, 2013	Interim Report	15	Dec, 2012	
Oct, 2014	Interim Report	20	Jun, 2013	Claims through Mar 2013 Labs through Dec 2012
Year 3				
Mar, 2015	Interim Report	27	Dec, 2013	Claims through Sep 2013 Labs through Dec 2012
Aug, 2015	Interim Report	32	Jun, 2014	Claims through Mar 2014 Labs through Dec 2013
Year 4				
Mar, 2016	Interim Report	39	Dec, 2014	Claims through Sep 2014 Labs through Dec 2013
Aug, 2016	Interim Report	44	Jun, 2015	Claims through Mar 2015 Labs through Dec 2014
Year 5				
Jun, 2017	Final Report	54	Dec, 2015	Claims through Dec 2015 Labs through Dec 2014

The reports will include a core set of analyses with corresponding tables and figures that repeat with updated data in each of the 6 monthly blocks.

The interim reports along with the draft and final reports will consist of a description of the methods, including patient selection and variable definitions. This description will be followed by tables for each of the anticoagulant medications, follow-up characteristics (including adherence) and the utilization measures of interest. The tables will be descriptive of all included medications and not include explicit comparisons. The tabular results will be followed by an interpretive summary along with a discussion of the findings and implications.

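### Section 3.6.1 places the utilization measures and non-persistence curves in a cohort matched to NOAC users within quarter, which gives no usable pre-launch baseline and does not describe warfarin use generally

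*Combined protocol and SAP*

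**What the plan says.** **The matched-only rule.** In section 3.6.1 (secondary outcomes), NOAC users are matched to warfarin users 1:1 on a propensity score, by nearest neighbour with a caliper of 0.05, and patients "will be matched within calendar quarters (3 month periods". The Table 3 measures "will be described for the PS-matched cohort". In the summary table that closes the section, the utilization row lists the matched cohort alone, while the baseline-characteristics row lists both unmatched and matched. The Protocol Changes table agrees with the current text: "these measures are examined in a propensity-score matched cohort, rather than in the overall study population". The reason given there is validity of comparison.

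**The role of pre-launch data.** Section 3.6.1 dates the dabigatran launch to October 2010. Sections 3.2 and 3.6.1 use the data before that date to characterize warfarin patients and any shift in their characteristics.

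**The aims.** The synopsis and section 2 set out to describe how warfarin and the NOACs are being used, including switching and discontinuation. Section 1 names the change in warfarin use after NOACs arrive as something to be understood.

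**Text that points the other way.** The synopsis (Data Analysis Methods) speaks of examining utilization overall, and the visible sentence then breaks off. Section 3.2.1 states that "with a projected 100,000 patients meeting selection criteria, the various adherence measures will be estimated" to within its precision target. The opening of section 3.6.1 promises updates on switching, discontinuation, adherence and persistence for the cohorts already identified. Core Tables 4 and 5 in Appendix 1 give adherence metrics for anticoagulation users without mentioning matching.

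**The concern.** Matching serves a between-drug contrast, but most of what this study promises is description. A cohort built by pairing each NOAC initiator with a warfarin initiator of the same quarter can hold no warfarin patient from a quarter with no NOAC on the market. In later quarters it holds only the warfarin patients selected as matches. Persistence and discontinuation in such a cohort describe warfarin patients chosen to resemble NOAC users. They do not describe warfarin patients as a whole.

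Two things are at stake. A change in warfarin persistence after NOAC introduction cannot be shown without a usable estimate from before it. A reader may also take the matched warfarin curve as the general pattern of warfarin use. In addition, section 8 says of the reports: "The tables will be descriptive of all included medications and not include explicit comparisons". Tables without explicit comparisons still place the drugs side by side, so matching keeps a purpose. That purpose does not require leaving out an unmatched description.

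**Working it through.** **Inputs**
- Accrual (section 3.2.1): "we assume that between 10,000 and 15,000 patients per year will meet selection criteria". This is a projection from UnitedHealth counts. Per quarter it is 10,000/4 = 2,500 to 15,000/4 = 3,750, assuming even accrual.
- Launch: October 2010 (section 3.6.1), so Q4 2010 is the first quarter in which a match is possible.
- Study data: 2009 to 2015. Base cohort: January 2009 to June 2012.
- Look-back (section 3.2): "The first dispensing is preceded by at least 12 months continuous enrollment in the study database". If that year must lie inside data starting January 2009, entry starts in Q1 2010. Section 3.2 also gives January 2009 as the start of initiation, so both cases are shown.

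**The plan's own precision figure.** By the section 3.2.1 formula, sqrt(p(1-p)/n), p = 0.20 and n = 10,000 give 0.40%, as in its Table 1.

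**Quarters and initiators with no possible match (per data source)**

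| | Entry from Q1 2010 | Entry from Q1 2009 |
|---|---|---|
| Quarters before Q4 2010 | 3 | 7 |
| Share of all accrual quarters | 3/24 = 12.5% | 7/28 = 25% |
| Share of base-cohort quarters | 3/10 = 30% | 7/14 = 50% |
| Initiators, low rate | 3 × 2,500 = 7,500 | 7 × 2,500 = 17,500 |
| Initiators, high rate | 3 × 3,750 = 11,250 | 7 × 3,750 = 26,250 |

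The plan's total of 100,000 over seven years implies 100,000/7 = 14,286 per year. That gives 14,286 × 9/12 = 10,714 or 14,286 × 21/12 = 25,000, inside these ranges.

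**Boundary case.** Launch falls in the first month of Q4 2010, and the day is not given. A warfarin initiator from early October could be matched to a later dabigatran initiator in that quarter. At most this is one month of accrual: 10,000/12 = 833 to 15,000/12 = 1,250 candidates before matching.

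**Precision of a pre-launch stratum.** With the smallest count, n = 7,500:
- p = 0.20: sqrt(0.2 × 0.8 / 7,500) = 0.46 percentage points.
- p = 0.50 (worst case): sqrt(0.25 / 7,500) = 0.58 percentage points.

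Both are within the 1% that section 3.2.1 expects for adherence measures. Censoring is ignored.

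**The case against.** **The plan does not name the matched cohort alone.** The synopsis, the opening of section 3.6.1, section 3.2.1 and core Tables 4 and 5 can all be read as whole-cohort reporting. This stands as a conflict to be reconciled. A reader might infer that unmatched utilization appears nowhere, and the documents do not support that. Even if Tables 4 and 5 are unmatched, however, they cover all periods combined or the latest period. The base cohort itself spans the launch, so neither table isolates a pre-launch stratum.

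**Text is redacted.** Several objectives, bullets and a core table are blank, and an unmatched run may be among them. This stands too. It does not remove the explicit matched-only wording and summary row, and if such a run exists they need to say so.

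**The choice was deliberate, and earlier reports may hold the baseline.** The change followed two interim reports, which appear to have used the overall population. MarketScan was added only in version 2.0, so those reports would not cover it. The same version shortened the discontinuation gap from 6 months to 30 days, so an earlier description would presumably use a different definition.

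**A pre-launch persistence baseline is not a listed deliverable.** This is fair: the change in utilization is named in the background, and the visible objectives do not demand a pre-launch stratum. The objectives do ask for a description of warfarin use, switching and discontinuation, and a matched subset does not give that for warfarin patients in general.

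**Switches by pre-launch starters may be reported elsewhere.** Table 3 defines a switch as "Dispensing of another anticoagulant within <30 days of the end of days supplied of the previous medication", which covers a pre-launch warfarin starter who later moves to a NOAC. These patients are outside the matched analysis, apart from the boundary case. A reader might infer that their switches are lost throughout. That is not established: core Tables 7-12 describe switchers and discontinuers without naming a population, and section 3.6.1 lists user characteristics as both unmatched and matched.

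**Conclusion.** The concern holds as a statement about what section 3.6.1 assigns. The matched cohort excludes warfarin initiators from every quarter before Q4 2010: 12.5% or 25% of accrual quarters, depending on when entry starts, and 30% or 50% of the base cohort's quarters. The patient counts rest on the plan's UnitedHealth projection, on even accrual, and on applying that rate to each data source.

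A reader might say that the cohort holds no pre-launch initiator at all. That is slightly too strong because of early October 2010, but a few weeks of possible matches make no usable baseline. A reader might also want the fraction of post-launch warfarin users retained. The documents give no NOAC share of initiations, so no figure is offered.

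The two primary outcomes, yearly initiation and user characteristics, are not affected. The point concerns the secondary utilization outcome. It is a worthwhile, inexpensive improvement together with a conflict to resolve, and it does not make the matched contrast invalid.

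**What to change.** 1. Report the Table 3 measures and the time-to-event curves in the unmatched cohort too, as description only, by drug and initiation period. Show warfarin initiators before October 2010 as their own stratum.
2. Keep the matched cohort for NOAC-versus-warfarin contrasts.
3. In the section 3.6.1 summary table, change the utilization population to *Unmatched (by drug and period) and Matched*, and bring the synopsis and the opening of section 3.6.1 into line.
4. State the population in the title of each core table and figure in Appendix 1.

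If redacted text already provides an unmatched run, steps 3 and 4 are enough to make that visible, provided the run separates pre-launch warfarin.

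The cost is one more set of tables and curves from data already processed, with no new data. Reports become longer, and the unmatched curves need a caution that they are not for comparing drugs.
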